1. INTRODUCTION

This statistical analysis plan (SAP) describes the analysis for Protocol AG-120-C-005, “A Phase 3, Multicenter, Randomized, Double-Blind, Placebo-Controlled Study of AG-120 in Previously Treated Subjects with Nonresectable or Metastatic Cholangiocarcinoma with an IDH1 Mutation,” Amendment 4, Version 5.0, which was issued on 04 April 2018. It contains definitions of analysis populations, derived variables, and statistical methods for the analysis of efficacy and safety.

This SAP provides a comprehensive and detailed description of the strategy, rationale, and statistical techniques to evaluate the necessary efficacy and safety endpoints. The purpose of this SAP is to ensure the credibility of the study findings by pre-specifying the statistical approaches to the analysis of study data prior to database lock. Pharmacokinetic (PK)/pharmacodynamic analysis and exploratory biomarker analyses are not in the scope of this SAP. This SAP will be finalized and approved prior to the database lock for the primary analysis.

2. STUDY OBJECTIVES

2.1. Primary Objective

The primary objective is:

- To demonstrate the efficacy of AG-120 based on progression-free survival (PFS) per Independent Radiology Center (IRC) assessment compared to placebo in subjects with nonresectable or metastatic cholangiocarcinoma with an isocitrate dehydrogenase 1 (IDH1) mutation.

2.2. Secondary Objectives

The secondary objectives are:

- To evaluate the safety and tolerability of AG-120 compared to placebo.
- To evaluate PFS per Investigator assessment.
- To compare the efficacy of AG-120 with placebo based on overall survival (OS), objective response rate (ORR), duration of response (DOR), and time to response (TTR), with response assessed per the Investigator and by the IRC.
- To evaluate health-related quality of life (HRQOL) with AG-120 compared to placebo as assessed by the European Organization for Research and Treatment of Cancer Quality of Life Questionnaires (EORTC-QLQ-C30 and EORTC-QLQBIL21), the Patient Global Impression of Change (PGI-C), and the Patient Global Impression of Severity (PGI-S).
- To evaluate health economic outcomes as assessed by the 5-level EuroQol five dimensions questionnaire (EQ-5D-5L).
- To evaluate the pharmacokinetics (PK) of AG-120.
- To evaluate the PK/pharmacodynamic relationship of AG-120 and 2-hydroxyglutarate (2-HG) in blood samples.

2.3. Exploratory Objectives

The exploratory objectives are:

- To evaluate, for the subgroup of placebo subjects who have crossed over to the AG-120 arm, the time from first dose of AG-120 to second documented progression on AG-120 or death, whichever occurs first (PFS2).
- To correlate baseline molecular and/or protein characteristics in tumor tissues with clinical response.
- To correlate baseline 2-HG levels in plasma samples with clinical response.
- To evaluate levels of mutant IDH1 and other genes in circulating tumor DNA obtained from plasma at baseline and over the course of the treatment.

AG120-C-005 Statistical Analysis Plan

- To correlate any PK variations with drug-metabolizing enzyme (DME) related genes, if the data are warranted.
- To explore additional biomarkers in blood for morphologic, functional, biologic, epigenetic, and metabolic changes over the course of treatment.

3. STUDY ENDPOINTS

3.1. Primary Endpoint

The primary endpoint is PFS, defined as the time from date of randomization to date of first documented disease progression (as assessed by the IRC per RECIST v1.1), or date of death due to any cause.

3.2. Secondary Endpoints

- Adverse events (AEs), serious adverse events (SAEs), AEs leading to discontinuation or death. The severity of AEs will be assessed by the National Cancer Institute Common Terminology Criteria for Adverse Events (NCI CTCAE), version 4.03.
- Safety laboratory parameters, vital signs, 12-lead electrocardiograms (ECGs), evaluation of left ventricular ejection fraction (LVEF), Eastern Cooperative Oncology Group (ECOG) performance status (PS), and concomitant medications.
- Secondary efficacy endpoints include:
 - OS, defined as the time from date of randomization to date of death.
 - ORR, defined as the proportion of subjects with a best overall response (BOR) defined as CR or PR, as assessed by the Investigator and by the IRC per RECIST v1.1.
 - DOR, defined as the time from date of first documented complete response (CR) or partial response (PR) to date of first documented disease progression or death due to any cause, as assessed by the Investigator and by the IRC per RECIST v1.1.
 - TTR, defined as the time from date of randomization to date of first documented CR or PR for responders, as assessed by the Investigator and by the IRC per RECIST v1.1.
 - PFS as determined by the Investigator.
- HRQOL as assessed by validated instruments (EORTC-QLQ-C30, EORTC-QLQBIL21, PGI-C, and PGI-S).
- Health economic outcomes as assessed by the EQ-5D-5L instrument.
- Serial or sparse blood sampling at specified time points for determination of plasma concentration-time profiles and PK parameters of AG-120.
- Blood sampling at specified time points for determination of 2-HG levels to characterize the pharmacodynamic effects of AG-120.

4. OVERALL STUDY DESIGN

This is a Phase 3, multicenter, randomized, double-blind, placebo-controlled efficacy and safety study of orally administered AG-120 in subjects with advanced cholangiocarcinoma (nonresectable or metastatic). Subjects, all personnel involved in the evaluation of subjects' response to treatment (eg, Investigators, study coordinators, study pharmacists), and designated Sponsor team members will be blinded to study treatment until documented disease progression.

Subjects are required to have a histologically consistent diagnosis of IDH1 gene-mutated cholangiocarcinoma that is not eligible for curative resection, transplantation, or ablative therapies. Subjects must have documented progression of disease and have received treatment with at least 1 but not more than 2 prior treatment regimens for advanced disease (nonresectable or metastatic). At least 1 of the prior regimens must have included gemcitabine or 5-FU. Systemic adjuvant chemotherapy will be considered a line of treatment if there is documented disease progression during or within 6 months of completing the therapy, with Sponsor approval.

A total of approximately 186 subjects will be randomized in a 2:1 ratio to the AG-120 and placebo arms, respectively, stratified by number of prior therapies (1 vs. 2). The primary analysis of PFS will occur once 131 PFS events have been determined by Investigator assessment. Overall survival will be analyzed twice, once at the time of PFS primary analysis and once at the occurrence of 150 OS events.

Subjects who meet all study eligibility criteria will be randomly assigned in a 2:1 ratio to receive AG-120 orally at a dose of 500 mg once daily (QD) or AG-120-matched oral placebo QD. Daily study treatment will begin on C1D1. Cycles are 28 days (+/-2 days) in duration and dosing is continuous. Study visits will be conducted every other week during Cycles 1-3 (Days 1 and 15), and Day 1 of each cycle thereafter. Radiographic assessment (computed tomography [CT] or magnetic resonance imaging [MRI]) for evaluation of disease response will be conducted every 6 weeks (± 5 days) for the first 8 assessments (ie, through week 48) and every 8 weeks (± 5 days) thereafter from C1D1, independent of dose delays and/or dose interruptions, and/or at any time when progression of disease is suspected.

Upon request by the Investigator, the subject and site staff will be unblinded to treatment assignment after documented disease progression (as assessed by the Investigator and after consultation with the Sponsor Medical Monitor), and subjects randomized to the placebo arm who continue to meet eligibility criteria determined in the End of Treatment (EOT) visit will be given the opportunity to cross over to the active treatment arm and receive AG-120. For those subjects who cross over, placebo will not be counted as a prior line of therapy for the purpose of eligibility. If subjects cross over, they will start again with study procedures as at C1D1. These subjects will continue to be evaluated for tumor response by the Investigator.

An independent data monitoring committee (IDMC) will review the safety data on a regular basis to ensure the safety of treatment and proper conduct of the study. The first interim safety review meeting will be conducted when approximately 20 subjects have completed 2 cycles of therapy or have discontinued earlier; thereafter, meetings will be conducted every 3-6 months or on an ad hoc basis. No formal interim analysis for efficacy will be conducted before the primary analysis.

5. SAMPLE SIZE ESTIMATION

A total of approximately 186 subjects will be needed for the study.

The primary objective of the study is to demonstrate the improvement in PFS by IRC assessment for subjects receiving treatment with AG-120 as compared to subjects receiving placebo.

Assuming a hazard ratio (HR) of 0.5 for PFS (equivalent to a median PFS of 3 months in the placebo arm vs. 6 months in the AG-120 arm, assuming an exponential distribution), a total of 131 PFS events are required to provide 96% power at a 1-sided alpha of 0.025 level of significance to reject the null hypothesis using a stratified log-rank test. Based on this, a total of approximately 186 subjects will need to be randomized in a 2:1 ratio to the AG-120 and placebo arms, respectively, assuming approximately a 22% dropout rate, an approximate 26-month randomization period, and an additional 6-month follow-up for PFS after the last subject is randomized. Therefore, the primary analysis of PFS will occur at approximately 6 months after the last subject is randomized.

Overall survival will be analyzed twice, once at the time of the final analysis for PFS and once at the occurrence of 150 OS events (final analysis for OS, which will occur at approximately 24 months after the last subject is randomized). Assuming an HR of 0.67 for OS (median OS of 8 months in the placebo arm vs. 12 months in the AG-120 arm, assuming an exponential distribution), a total of 150 OS events will provide 64% power at a 1-sided alpha of 0.025.

6. ANALYSIS POPULATIONS

The following subject populations (ie, analysis sets) will be evaluated and used for presentation of the data:

- Intent-to-Treat Set (ITT)
- Safety Analysis Set (SAS)
- Per-Protocol Set (PPS)
- Crossover Set (COS)

6.1. Intent-to-Treat Set (ITT)

All subjects who are randomized, with the treatment group designated according to the randomization. The ITT will be the primary analysis set for all analyses except for safety.

6.2. Safety Analysis Set (SAS)

All subjects who receive at least one dose of study drug (AG-120 or placebo). Subjects will be analyzed according to the actual treatment received. The SAS will be the primary analysis set for all safety analyses.

6.3. Per-Protocol Set (PPS)

All subjects in ITT who do not violate the terms of the protocol in a way that would significantly affect the study outcome, with treatment group designated according to the randomization.

In general, subjects who meet the following criteria will be excluded from this analysis set:

- Do not have histopathologically diagnosed nonresectable or metastatic cholangiocarcinoma
- Do not have documented IDH1 gene-mutated disease based on central laboratory testing
- Do not have any measurable lesion at baseline as defined by RECIST v1.1 as determined by IRC
- Three or more prior systemic therapy in an advanced setting (nonresectable or metastatic)
- Have received a prior IDH inhibitor.

6.4. Crossover Set (COS)

A subset of placebo subjects who cross over and receive AG-120 upon the radiographic documented progression (PD). The COS will be the analysis set for analyzing post-crossover data.

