Primary Endpoint Results and Subsequent Study Unblinding: Once the primary endpoint of PFS (based on central radiology RECIST 1.1 assessment) is statistically analyzed, the Sponsor will communicate the topline aggregate results of the study via public disclosure, which will include participating study teams. Shortly after public disclosure of the topline aggregate results, the Sponsor will communicate to all sites that treatment assignments of all subjects will be unblinded and will also inform sites which of the 2 following scenarios to pursue following unblinding.

If the primary endpoint is statistically positive, all ongoing subjects (AG-120 and placebo-treatment assigned subjects) will be given the opportunity to receive open-label AG-120 following unblinding. Unblinding will no longer be contingent upon documented radiographic disease progression. Subjects who were already receiving AG-120 may continue to receive AG-120 on the same assessment schedule. Subjects who were receiving placebo and continue to meet cross-over eligibility criteria will be given the opportunity to receive open-label AG-120. For subjects who cross over, placebo will not be counted as a prior line of therapy for the purpose of eligibility. If subjects cross over, they will follow the same assessment schedule as

from CID1. Prior to crossing over, these subjects will undergo a CT or MRI that will serve as the new baseline against which all subsequent RECIST v1.1 assessments will be performed. If the subject has undergone a recent CT or MRI (≤ 3 weeks prior to start of cross-over treatment), the scan does not need to be repeated. Palliative radiotherapy to treat symptomatic pre-existing or new non-target lesions (per RECIST v1.1) that cannot otherwise be medically managed will be permitted after unblinding has occurred. AG-120 should be held for the duration of palliative radiotherapy. A 2-week washout from completion of radiotherapy will be required prior to starting or resuming AG-120. For subjects receiving palliative radiotherapy prior to the first dose of open-label AG-120, a repeat CT or MRI will be performed upon completion of the 2-week washout period to document the area that was irradiated and to serve as the new baseline. All decisions to pursue palliative radiotherapy will require Sponsor and/or Medical Monitor approval.

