If the primary endpoint is statistically positive, all ongoing subjects (AG-120 and placebo-treatment assigned subjects) will be given the opportunity to receive open-label AG-120 following unblinding. Unblinding will no longer be contingent upon documented radiographic disease progression. Subjects who were already receiving AG-120 may continue to receive AG-120 on the same assessment schedule. Subjects who were receiving placebo and continue to meet cross-over eligibility criteria will be given the opportunity to receive open-label AG-120. For subjects who cross over, placebo will not be counted as a prior line of therapy for the purpose of eligibility. If subjects cross over, they will follow the same assessment schedule as from C1D1. Prior to crossing over, these subjects will undergo a CT or MRI that will serve as the new baseline against which all subsequent RECIST v1.1 assessments will be performed. If the subject has undergone a recent CT or MRI (≤ 3 weeks prior to start of cross-over treatment), the scan does not need to be repeated. Palliative radiotherapy to treat symptomatic pre-existing or new non-target lesions (per RECIST v1.1) that cannot otherwise be medically managed will be permitted after unblinding has occurred. AG-120 should be held for the duration of palliative radiotherapy. A 2-week washout from completion of radiotherapy will be required prior to starting or resuming AG-120. For subjects receiving palliative radiotherapy prior to the first dose of open-label AG-120, a repeat CT or MRI will be performed upon completion of the 2-week washout period to document the area that was irradiated and to serve as the new baseline. All decisions to pursue palliative radiotherapy will require Sponsor and/or Medical Monitor approval.

If the primary endpoint is statistically negative, all ongoing AG-120 subjects will be permitted to continue receiving open-label AG-120 following unblinding at the discretion of the treating investigator. Palliative radiotherapy will be allowed for subjects who continue receiving AG-120 as described in the preceding “statistically positive” paragraph. Subjects who were receiving placebo will not be permitted to receive open-label AG-120 in this scenario and will come off study.

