12.3. Analysis Sets

The following analysis sets will be evaluated and used for presentation of the data:

- Intend-to-Treat Analysis Set (ITT): All subjects who were randomized. Subjects will be classified according to the assigned treatment arm. The ITT will be used for the primary efficacy analyses, and is the default analysis set unless otherwise specified.

- Safety Analysis Set (SAS): All subjects who received at least one dose of study treatment. Subjects will be classified according to the treatment received. The SAS will be the primary set for the analysis of safety data, unless otherwise specified.
- Crossover Set (COS): A subset of subjects initially assigned to receive placebo who crossed over and received AG-120.
- Per-Protocol Set (PPS): All subjects in the ITT who had no major protocol violations. Additional efficacy analyses may be produced using the PPS. Rules for major protocol violations will be specified in the statistical analysis plan (SAP).
- Pharmacokinetic Analysis Set (PAS): All subjects who have at least 1 blood sample post-dose providing evaluable PK data for AG-120.

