15.10. Protocol Amendment History

Changes that had a major impact on the conduct of the study are summarized here.

Amendment 5, Version 6.1 (South Korea only):

- Added language to outline the management of subjects following study unblinding.

- Added an exclusion criterion to exclude subjects with a known medical history of PML.
- Added new Section 11.3 (Other Potential Risks) describing leukoencephalopathy and sensorimotor neuropathy/polyneuropathy as other potential risks associated with AG-120.

Amendment 5, Version 6.0 (Global except South Korea):

- Added language to outline the management of subjects following study unblinding.
- Added an exclusion criterion to exclude subjects with a known medical history of PML.
- Added new Section 11.3 (Other Potential Risks) describing leukoencephalopathy and sensorimotor neuropathy/polyneuropathy as other potential risks associated with AG-120.

Amendment 4, Version 5.2 (France only):

- Added a new exclusion criterion to exclude subjects with a known medical history of progressive multifocal leukoencephalopathy (PML).
- Added a new Section 9.8.1.2 (Dose Suspension Criteria).
- Added a new Section 9.10 (Other Potential Risks).

Amendment 4, Version 5.1 (South Korea only):

- Added the Patient Global Impression of Change (PGI-C) and the Patient Global Impression of Severity (PGI-S) as additional health-related quality of life (HRQOL) measures throughout the protocol, per Food and Drug Administration's (FDA's) request to include anchor-based questions in addition to the European Organisation for Research and Treatment of Cancer - Quality of Life Questionnaire – Core Questionnaire (EORTC-QLQ-C30) and the European Organisation for Research and Treatment of Cancer - Quality of Life Questionnaire - Cholangiocarcinoma and Gallbladder Cancer Module (EORTC-QLQ-BIL21).
- Removed abstinence as a form of contraception; removed “highly” from the phrase, “use a highly effective form of contraception;” and clarified what forms of contraception fit the definition of “effective forms of contraception,” per United Kingdom (UK) requests.
- Added the following caveat to Exclusion Criterion 17: “Subjects with chronic HBV that is adequately suppressed per institutional practice will be permitted.”

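### The SAP's Crossover Set admits only placebo subjects who cross over at radiographic progression, so the few who cross over without it after study unblinding drop out of the outputs built on that set

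*SAP*

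**What the plan says.** The two documents define the same analysis set differently.

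- SAP 6.4 defines the COS as placebo subjects "who cross over and receive AG-120 upon the radiographic documented progression (PD" and adds: "The COS will be the analysis set for analyzing post-crossover data".
- Protocol 12.3 defines it as "A subset of subjects initially assigned to receive placebo who crossed over and received AG-120". Progression is not mentioned.

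The current protocol has two crossover routes. The first is crossover after investigator-assessed progression and unblinding of the individual subject. The second opens after a positive primary result, when the whole study is unblinded. For that case Protocol 7.1 states: "Unblinding will no longer be contingent upon documented radiographic disease progression". Protocol 9.6 adds: "Subjects who were receiving placebo and continue to meet cross-over eligibility criteria will be given the opportunity to receive open-label AG-120".

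The SAP introduction names its reference version as "Amendment 4, Version 5.0, which was issued on 04 April 2018". The amendment history (Protocol 15.10) places the second route under Amendment 5: "Added language to outline the management of subjects following study unblinding". SAP 8.3, 8.8 and Appendix C describe only crossover at progression. SAP 11, which lists departures from the protocol, mentions only the PK set and PK analyses.

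**The concern.** If progression at crossover is the only route, the two COS definitions select the same people. Once the second route exists they do not. A placebo subject who starts open-label AG-120 without progression is in the protocol's COS but not in the SAP's.

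SAP 7 makes the COS the default set for after-crossover data and ends the placebo contribution to the before-crossover period at crossover. Under that default, such a subject leaves one period without entering the other. The final report could then understate how many placebo subjects crossed over, omit their response and progression data on AG-120, and leave programmers to decide whether they count in the after-crossover safety column.

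A related wording gap concerns PFS2. Protocol 12.12.1 counts time to a second documented progression and takes the pre-crossover progression scan as the usual baseline. A subject who crosses over without progression has neither a first progression nor such a scan.

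**Working it through.** **1. Which outputs depend on the COS**

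| Output | Set or wording | Subject crossing over without progression |
|---|---|---|
| Crossover disposition (SAP 7.1) | COS | Left out |
| Post-crossover PFS2, ORR, TTR, DOR (SAP 8.8) | COS, through SAP 6.4 and 7 | Left out |
| After-crossover tables with no set of their own, e.g. concomitant medications (SAP 7.5) | COS by default; the text itself depends only on the start of AG-120 | Left out if the default is applied |
| Safety column for AG-120 after crossover (SAP 9) | Safety Analysis Set; column membership not defined against the COS | Unclear |
| Total AG-120 safety column (SAP 9) | Everyone ever dosed with AG-120 | Included |
| AE listings (SAP 9.1) | All AEs | Included |
| Exposure after crossover (SAP 7.6) | Placebo subjects who crossed over and received AG-120 | Included |
| OS (SAP 8.3) | ITT, with data after crossover | Included |

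The unclear row arises because SAP 9 describes total AG-120 both as everyone ever dosed and as the sum of the as-dosed and after-crossover groups. These agree only if the after-crossover group has no progression condition. SAP 6.4 and 7 point the other way.

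**2. How many subjects**

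The documents give no figure for this group, so it is estimated from the design.

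Inputs:
- 62 placebo subjects (Protocol 8.1)
- placebo median PFS 3 months, exponential (SAP 5)
- accrual 5 per month for 6 months, then 8 per month (Protocol 7.1), one third to placebo
- primary analysis at about month 32 (Protocol 12.7.1)
- dropout 22% (Protocol 12.2)

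As a check on the design, the Schoenfeld formula with 131 events, HR 0.5 and 2:1 allocation gives a power of 96.2%, against the stated 96%.

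Accrual ends at 6 + (186 − 30)/8 = 25.5 months. With hazard λ, the expected number of placebo subjects still progression-free at month c is

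N(c) = (8/3)/λ × [e^(−λ(c−25.5)) − e^(−λ(c−6))] + (5/3)/λ × [e^(−λ(c−6)) − e^(−λc)].

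- No dropout: λ = ln 2/3 = 0.2310. N(32) = 11.54 × (0.2227 − 0.0025) + 7.21 × (0.0025 − 0.0006) = 2.54 + 0.01 = 2.55, or 4.1% of 62.
- With dropout, read (an assumption) as a competing exponential hazard that accounts for 22% of exits: added hazard 0.2310 × 0.22/0.78 = 0.0652, total 0.2962. N(32) = 9.00 × (0.1458 − 0.0005) + 0.002 = 1.31, or 2.1% of 62.
- If study unblinding came three months after month 32 (an assumption), the range is 0.54 with dropout to 1.28 without.
- If the placebo median were 2 months (assumed), month 32 gives 0.33 to 0.81. If it were 4 months (assumed), 2.81 to 4.88.

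These figures count subjects without progression. They do not remove those who fail the crossover eligibility criteria or decline AG-120, so the number who cross over would be lower.

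**The case against.** **The default yields to other rules.** The COS default in SAP 7 gives way wherever another rule is specified, and SAP 9 specifies the Safety Analysis Set. A reader might infer that these subjects vanish from every post-crossover table and that their AG-120 adverse events are lost. The documents do not support that. The total AG-120 column, the AE listings, the exposure table and OS all keep them. A mismatch between total AG-120 and the sum of its parts would arise only if the COS condition were carried into the safety section. This objection stands, and it confines the point to the COS-based outputs and the unclear safety column.

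**PFS2 is largely workable already.** SAP 8.8 defines it as PFS per Investigator with tumor measurements re-baselined before crossover. Protocol 7.1 and 9.6 require a new baseline scan unless one was done within the previous 3 weeks, and Protocol 12.12.1 uses the latest scan before the first AG-120 dose if there is more than one. A reader might infer that PFS2 cannot be derived for these subjects. It can. Only the reference to a second progression does not fit them.

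**Timing.** The SAP follows the version it cites, and the second route opens only after the primary analysis and only if that is positive. No such subject can exist in the primary PFS analysis. That stands, but the final report will still need a definition that covers both routes.

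**A progression-only set may be preferable for efficacy.** Pooling subjects who start AG-120 at progression with subjects who start before it mixes two populations. That is a fair argument for showing the routes separately. It does not justify an undeclared departure from Protocol 12.3 in a set that also drives disposition.

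**Conclusion.** The point holds as an unreconciled definition with limited reach. SAP 6.4 is narrower than Protocol 12.3, the difference is not declared in SAP 11, and the current protocol creates subjects who fall between the two. The consequences are an incomplete crossover disposition summary, incomplete post-crossover efficacy, and an unresolved conflict between SAP 6.4 and 7 on one side and SAP 9 on the other over who is in the after-crossover safety column.

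The expected size is about 1 to 3 of 62 placebo subjects. This rests on the planned accrual, a 3-month exponential placebo median and analysis at month 32. It runs from 0.3 to 4.9 for assumed medians of 2 to 4 months, with and without dropout. Only the final study report is affected. Primary PFS and OS are not, and there is no loss of AG-120 safety data from the totals or listings. The issue is minor, but worth correcting because the remedy is simple.

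**What to change.** Before the final study report, amend the SAP as follows:

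1. Replace the SAP 6.4 definition with that of Protocol 12.3: any subject assigned to placebo who crossed over and received AG-120. State that the AG-120 after-crossover column in SAP 9 has the same membership among dosed subjects.
2. Update the protocol reference in SAP 1 to Amendment 5, and bring the crossover descriptions in SAP 8.3, 8.8 and Appendix C into line with it.
3. Add a flag for the crossover route: progression or study unblinding.
4. State the PFS2 rule for subjects who cross over without progression. Either the event is the first progression or death after the first AG-120 dose, or these subjects are excluded from PFS2 only. Align the reference to a second progression in Protocol 12.12.1 with the choice made.

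The cost is SAP wording and one derived variable. The downside is that post-crossover efficacy would combine two routes with different disease status at the start of AG-120. The flag lets them be shown separately, and with so few subjects a listing may be enough for the unblinding route.
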